4.4. Treatment Compliance

It is expected most subjects enrolling in the study will complete both treatment visits. Since the treatments are to be administered to the subject and supervised, compliance with the protocol is expected.

4.5. Randomization Procedures

Subjects will be stratified randomly by sex and age groups. Subjects will be allocated random sets of serial numbers kept on a master list which will be retained in a secured location. The faculty member grading the photographs will be given the 440 photographs completely in random order, randomized by the primary investigator.

5. STUDY METHODOLOGY

5.1. Preparation of Investigational Products

The dry components of each rinse will be formulated prior to study and placed in a plastic vial with lid. The statistician will generate a second randomization list to identify which vial (A or B) the patient will receive at the first and second visits, respectively.

Prior to beginning the study, the dry powdered components for each treatment rinse will be weighed and placed into clean 20 mL vials, (for both the enzymatic and placebo rinse) and sealed with plastic caps. This will prevent contamination or spillage. All vials will be prepared at one time in a clean room prior to the study.

Selected committee members will measure out one gram of enzyme and one gram of placebo (powdered sugar) for each subject. Both the placebo and the proteolytic rinse compounds will be weighed, formulated and placed into darkened 20 mL vials with a plastic top. Each vial will then be assigned the appropriate code (Product A or Product B) by the co-investigator [name] Only this investigator ([name]) will know the identity of the vial contents and will share this information with the statistician at the time of statistical analysis. The formulated compounds placed in the clean vials will be stored in a locked secured location.

Manufacture of Bromelain Rinse:

The bromelain enzyme will be obtained (donated) in bulk powder form from Ultra Bio-logics Inc. (Chateauguay, Quebec, Canada). The Ultra Bio-logic bulk bromelain concentrated supplement is standardized (by manufacturer) to 2400 Gelatin Digesting Units (GDU)/gram. The strength of an enzyme is quantified in GDU/gram units. GDU/gram tells us how much protein a gram of bromelain can digest. The proteolytic rinse will contain one gram of bromelain brought into solution with 15ml of pineapple juice. One gram of bromelain is within the recommended daily dosage for oral consumption by the manufacturer-

Bromelain is stable at room temperature for more than a year in its dry form. It is active when reconstituted with warm water. (In this study- warm pineapple juice will be substituted for warm water). Since bromelain is active in the liquid form, the rinse will be constituted with canned pineapple juice just prior to administration while ensuring complete dissolution. Bromelain's enzymatic activity is destroyed by the pasteurization process during canning. Thus, the canned pineapple juice has the correct pH for optimal activity but does not contribute any enzymatic activity to the test solution.

Bromelain's optimal activity is at 55°C. This is approximately the temperature of very warm coffee. To achieve optimal results a temperature controlled hot plate will be used to keep a pot of warm pineapple juice at 50°C available to mix with the powdered mixture just prior to administration.

Manufacture of Placebo Rinse:

The placebo rinse will consist of powdered sugar and pineapple juice. Powdered sugar has the same color and consistency as the bromelain powder. This placebo will not be discernible once weighed and placed in sealed vials. Canned pineapple juice contains no active bromelain, which is destroyed in the pasteurization process.

The components of the two study rinses are as follows:

TREATMENT A: Placebo	TREATMENT B: Proteolytic Rinse
Pineapple juice (15 mL)	Pineapple juice (15 mL)
Powdered sugar (1.0 gm)	Bromelain powder (1.0 g)

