2. STUDY DESIGN

This will be a single site, cross-over, double-blind study with up to 55 subjects enrolled in the study. Since each person varies with technique and diligence in brushing their teeth, each subject will serve as their own control in this cross-over study. There will be at least a week time interval between the two arms of the study (length of wash out phase: one week). The study will be completed over the course of two weeks. Each step in the protocol will be timed to reduce inter- and intra-subject variability. Toothbrushes used in the study will be uniform, a new tooth brush will be used at each arm of the study. All oral hygiene aids will be of the same brand to eliminate variability (eg: all toothbrushes will be of the same brand, all disclosing tablets of the same brand, etc). For standardization and optimal photography, the same type of cheek retractor and digital camera will be used for all subjects.

Hypothesis

Null: There is no statistically significant difference in visual plaque scores with or without use of a proteolytic enzyme rinse aid.

Alternative: There is a statistically significant difference in visual plaque scores with use of proteolytic enzyme rinse aid.

Product Description

This study will use bromelain as the proteolytic enzyme in the oral rinse. Bromelain is an enzyme naturally found in high concentration in the stem of pineapples. This proteolytic, proteindigesting enzyme breaks down (hydrolyzes) proteins by reducing large complex proteins into smaller peptides or individual amino acids (25). For this reason, bromelain is commonly used as a digestive aid, (in pill form) or (in powder form) as a meat tenderizer.

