4. TEST TREATMENTS

4.1. Administration of Study Investigational Product

The components of each treatment will be formulated prior to treatment and placed in a plastic vial. Each of the vials for the oral rinse treatments will be labeled with a unique set of numbers for subject and stage of treatment (only decoded by use of master list).

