4.2. Blinding/Unblinding Procedures

To eliminate potential human bias, photos will be graded independently by one examiner from Indiana University School of Dentistry with dental clinical experience. The examiner will be blinded with regard to the stage and visit of the oral hygiene procedures. The identification on the photos will not allow the examiner to know which photos came from the same subject, which series they are evaluating (baseline staining, post-rinse, post-brush, post-Waterpik) and which treatment.

Each photo will be independently reviewed and scored assessing the degree of plaque staining from one to five. An example photograph of each degree (1-5) will be given to the examiner for standardization.

The researchers and subjects will be blinded to knowing which vial has the proteolytic enzyme treatment. The subsequent visit the subject will receive the second vial. The study records will be maintained by this committee member ([name]).

Each photograph will be labeled by only a serial number and can only identified through use of a master sheet. Each subject will have eight randomly assigned serial numbers corresponding to each testing step and visit (two different study visits with four photographs each).

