5.2. Clinical Procedures

All study materials needed for each test subject will be contained in a new cardboard box. Each box will contain:

- Vial of enzyme powder with attached set of assigned random numbers
- Vial of placebo powder with attached set of assigned random numbers
- 10 disposable cheek retractors
- Two disclosing tablets for staining
- Waterpik device
- Two toothbrushes (pre-pasted and individually sealed by manufacturer)

After explaining the experiment in obtaining consent (either by phone or in person), the subject will be randomized and given their assigned study box. The subject will then put their name on the outside of the box and on the box of the Waterpik. The name on the outside of the box will allow for retrieval for the second visit. The student researcher will then record the first serial number with the name of the test subject. This will be entered on the master list. The master list will then have been pre-prepared and grouped into 55 patient sets. Each set of random numbers for each patient will be divided and assigned with four numbers attached to each test vial. At the completion of the first visit, the cardboard box containing the Waterpik and the remaining materials will be sealed with adhesive tape and secured in a locked room. When the patient returns for their next testing visit, that subjects' box will be retrieved and the second vial labeled with the subject's second set of numbers will then be used. The test procedure will be repeated as with the first visit as described in 2.1.

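### Section 5.1 prints what reads as the key to the study-wide A/B vial code, although it says only one co-investigator will know the vial contents

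*Combined protocol and SAP*

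**What the plan says.** Section 2 describes the design: "This will be a single site, cross-over, double-blind study with up to 55 subjects enrolled in the study". Section 4.2 says who is to be blind: "The researchers and subjects will be blinded to knowing which vial has the proteolytic enzyme treatment".

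Section 5.1 sets up the code. It says "Each vial will then be assigned the appropriate code (Product A or Product B", and has the statistician produce a second randomization list "to identify which vial (A or B) the patient will receive at the first and second visits". One co-investigator alone is to know the contents, and tells the statistician only when the analysis is done. Further on, section 5.1 sets out the composition of the two rinses in a table. One column is headed "TREATMENT A: Placebo" and the other names the proteolytic rinse as Treatment B.

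On labels and lists:

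- Section 4.1 says the vials are "labeled with a unique set of numbers for subject and stage of treatment (only decoded by use of master list".
- Section 5.2 says "The student researcher will then record the first serial number with the name of the test subject", and that this goes onto the master list. It does not say who makes the entry.
- Section 4.5 keeps the master list in a secured place without saying who may read it.
- Section 1.3.1 describes a master list that links subject to study number.

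At the visit, the student investigator mixes the rinse (section 2.1, step g) and checks every photograph for diagnostic quality (section 9.4).

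**The concern.** A two-letter code protects a blind only while the meaning of the letters is kept from those who see them. Section 5.1 restricts that meaning to one person and then prints, in a document that visit staff work from, a table that reads as the key. Because the code is shared by the whole study, learning it once is enough for every vial whose letter, or whose place on the order list, can be seen.

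The exposure lies in trial conduct. Brushing and water-jet use come after the rinse and depend on effort, and photographs are then accepted or retaken. A difference that arises at those steps is already in the image, so the masked grader cannot remove it. The crossover does not remove it either: using each subject as their own control cancels stable differences between people, but not handling that differs by treatment. The power statement in section 8.1 concerns the score after the water jet, which follows all of these steps.

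**Working it through.** **The text, side by side**

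| Question | What the documents give | What they leave open |
|---|---|---|
| Who knows the contents? | One co-investigator, until analysis (5.1) | – |
| What do A and B mean? | Treatment A is placebo, Treatment B is enzyme (5.1 table) | Whether Product A/B is the same as Treatment A/B |
| Where is the letter seen? | Each vial is assigned a letter; a list gives A or B by visit (5.1) | Whether the letter is on the label; who matches vial to list, and where |
| What is on the vial? | Serial numbers (2.1 step f, 4.1, 5.2) | Whether anything else is |
| What does the master list decode? | Subject and stage of treatment (4.1); subject to study number (1.3.1) | Whether it shows treatment; who may read it |

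The first two rows conflict if the two pairs of letters are the same. The conflict matters in practice only if someone at the visit sees a letter or the order list. Section 5.1 requires someone to match letters to vials and does not place that step away from the visits. Step f of section 2.1 adds to the uncertainty: there the subject picks a vial, so it is not clear how the A/B order is carried out at all.

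**Number of vials:** 55 subjects × 2 = 110.

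**The plan's own power figure**

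Inputs from section 8.1: SD 1, correlation 0.5, difference 0.5, 45 completers, two-sided 5% paired t-test.

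- SD of the paired difference = √(2 × 1² × (1 − 0.5)) = 1.0.
- Noncentrality = 0.5 / 1.0 × √45 = 3.35, on 44 degrees of freedom.
- Power = 0.907, which agrees with the stated 90%.

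**Illustration of an assumed shift**

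Use the same test, with no enzyme effect and a shift b in the paired mean caused by knowledge of treatment. The noncentrality is b × √45. The documents give no value for b.

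| Assumed b | b as a share of 0.5 | Probability of rejection |
|---|---|---|
| 0.05 | 0.10 | 0.06 |
| 0.10 | 0.20 | 0.10 |
| 0.15 | 0.30 | 0.17 |
| 0.20 | 0.40 | 0.26 |
| 0.25 | 0.50 | 0.37 |

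**The case against.** The best case for the plan is that nothing in it puts a letter on a vial. Section 5.1 says a code is assigned, not printed, and every place that describes what is physically attached to the vial (section 2.1 step f, sections 4.1 and 5.2) describes numbers. The number sets are prepared in advance, so the A/B order could be settled at packing by the unblinded co-investigator. Someone who holds only serial numbers and the composition table learns nothing. This stands: the printed table does harm only together with a visible letter or the order list.

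A reader might also infer that the student holds the list that unmasks the vials. The documents do not support that. In section 4.1 the decoding relates to subject and stage, section 1.3.1 describes a link from subject to study number, the A/B order is on a separate list, and section 5.2 does not say who writes on the master list. No section gives that list a treatment column. Equally, no section rules one out or says who has access, so this is a possible route and no more.

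Safeguards during the visit also count. Brushing and water-jet instructions are scripted, each step is timed at two minutes, device pressure is fixed, photograph acceptance has written criteria, and subjects are meant to be blind. These limit the room for bias but do not replace concealment, because effort within two minutes and judgement of a photograph still vary.

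**Conclusion.** The point holds as an internal conflict in section 5.1 that leaves the double blind without clear protection. The section says one person will know the contents of coded vials, and it prints what is naturally read as the meaning of the code. The conclusion rests on one unstated step, that Product A/B equals Treatment A/B. Actual unmasking needs a second: that visit staff see the letters or the order list.

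It would go too far to say that vials carry the letters, that the student has the treatment key, or that the blind is broken for all 110 administrations; the text establishes none of these. Any bias is of unknown size. The false-positive rates of about 17% and 37% depend wholly on assumed shifts of 0.15 and 0.25 and show only that a shift well below the target difference of 0.5 would matter. The power calculation is not in question. The correction is worth making because it is specific and nearly free.

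**What to change.** 1. Use no A/B letter on vials or visit records, and head the two columns of the composition table simply placebo and enzyme.
2. Label each vial with subject number, visit 1 or visit 2, and the serials already planned. The unblinded co-investigator packs the kits from the statistician's list. Reword step f of section 2.1 so that the vial for that visit is taken, in line with the list.
3. State that the serial-to-treatment key is a separate file, closed to visit staff, held by the co-investigator and released to the statistician at analysis. State what the master list contains and who may read it.
4. Give the student a log of name, subject number and vial serial with no treatment column, so that the recording required in section 2.1 step f and section 5.2 can still be done.

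Cost: different labels on 110 vials, one extra file and a few changed sentences, provided this is done before kits are packed. Sample size, visits and analysis do not change.

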5.2. Clinical Procedures

All study materials needed for each test subject will be contained in a new cardboard box. Each box will contain:

- Vial of enzyme powder with attached set of assigned random numbers
- Vial of placebo powder with attached set of assigned random numbers
- 10 disposable cheek retractors
- Two disclosing tablets for staining
- Waterpik device
- Two toothbrushes (pre-pasted and individually sealed by manufacturer)

After explaining the experiment in obtaining consent (either by phone or in person), the subject will be randomized and given their assigned study box. The subject will then put their name on the outside of the box and on the box of the Waterpik. The name on the outside of the box will allow for retrieval for the second visit. The student researcher will then record the first serial number with the name of the test subject. This will be entered on the master list. The master list will then have been pre-prepared and grouped into 55 patient sets. Each set of random numbers for each patient will be divided and assigned with four numbers attached to each test vial. At the completion of the first visit, the cardboard box containing the Waterpik and the remaining materials will be sealed with adhesive tape and secured in a locked room. When the patient returns for their next testing visit, that subjects' box will be retrieved and the second vial labeled with the subject's second set of numbers will then be used. The test procedure will be repeated as with the first visit as described in 2.1.

5.3. Informed Consent Process

Informed consent will be obtained from subjects and two parents (if the subject is a minor <18 yrs and if 2^{nd} parent is reasonably available within the CFR regulations) prior to participation in study either in person or by phone (see 10.2). Assent will be obtained from all children under age 18. For children 14 to 17, the adult consent will be used as the assent form.

5.4. Oral Photography Process

Standardization of photographs: all photographs will be taken from the same angle (frontal), to include only the teeth and lips of the subject, with a single use, hands-free cheek retractor. Subject will be partially open so that the lower dentition is fully visible for photography. Each photograph will be at the same magnification (see 10.4). The adhesive label with the corresponding serial number will be placed on the subject's chin and will be included in the photograph.

6. EFFICACY MEASUREMENTS AND EVALUATIONS

6.1 Training & Calibration of Examiner:

One examiner from the Department of Periodontics and Allied Dental Programs or Cariology, Operative Dentistry and Dental Public Health, will be recruited to assess the plaque index of the digital photographs. An example of five oral photographs with varying degrees of stained adherent dental plaque will be graded according to the Orthodontic Plaque Index and used as a reference in grading the study photographs. The examiner will independently grade the residual plaque in each photograph.

The examiner will first be calibrated by scoring 10 randomly selected images and re-score the same images after a one week washout period. Once reliability testing of the examiner is at 0.8 or higher as measured by the intra-class correlation coefficient, the examiner will proceed to judge each photograph of the study.

6.2. Dental Plaque Evaluation and Data Management

Teeth will be disclosed and the facial tooth surfaces will be graded for visual plaque. Incisors (#s: 7-10 and 23-26) will be visually evaluated on digital photographs and assigned a score (0-4) according to the orthodontic plaque index (see figure 1 below). Examiner will be given a visual scale of comparison, which corresponds with the Orthodontic Plaque Index (OPI) for diagnosing dental plaque around orthodontic brackets. Each tooth will each receive an individual score, in addition all tooth scores will be added together to calculate a composite score for upper incisor and lower incisor segments. All recorded plaque scores will be recorded in an excel document on a password protected laptop computer by the grader.

To eliminate potential human bias, a single examiner from the Indiana University School of Dentistry with clinical dental experience, will judge each photograph. This examiner will be

blinded with regard to the stage of the oral hygiene procedure as described above.

Data/digital photographs will be viewed on the same computer and will be backed up daily onto a secure box.iu.edu health account, which will only be accessible to researchers and by two step authentications and passphrase. Research laptop will remain in secure location and locked whenever not in use.

Plaque scoring:

Figure 1: Orthodontic Plaque index scoring system(Beberhold).

6.3. Retention of Photographs

Digital photographs and any study material will be maintained for seven years following the completion of this study, as per Indiana law. Paper records will be stored in locked cabinets that only study personnel can access. Electronic records will be stored in encrypted, password protected files only accessible by study personnel.

7. ASSESSMENT OF SAFETY

7.1. Study Safety Management

The PI will be notified immediately if a serious adverse event occurs. An adverse event will be considered any unfavorable and unintended sign, symptom or disease associated with the use of the bromelain (investigational product) or the conduct of the study.

All adverse events will be reported to the IRB during annual review.

All serious adverse events will be reported immediately to the IRB. Serious adverse events include: any event resulting in death, is life-threatening, requires hospitalization, results in disability/permanent damage, congenital anomaly/birth defect, or requires intervention to prevent permanent impairment or damage, and/or other medical events(31).

7.2. Medical/Dental Monitor

The principal investigator and student investigator will be responsible for overseeing the conduct of the study.

7.3. Specification of Safety Parameters

The temperature of the pineapple juice (to reconstitute the solutions) will be monitored to make sure it is 50°C plus or -1°C. The formulated compounds placed in the clean vials will be stored in a locked secured location.

7.4. Methods for Assessing Safety Parameters

Each subject will be given the student investigator's phone number to call if they should experience any discomfort or unusual symptoms. On the second visit each subject will be questioned as to whether they experienced any discomfort or symptoms from the treatment at the first visit and an oral soft tissue exam will be completed.

7.5. Safety Oversight Plan

All subjects will receive a follow- up phone call the night of the study and reminded of the contact phone number of the student investigator in case of emergency or adverse side-effects. Subject will be instructed to make contact, should they experience any discomfort or unusual symptoms. This is part of the study's safety plan to assure the subjects are not reacting negatively to the product.

On the second visit each subject will be questioned as to whether they experienced any discomfort or symptoms from the treatment (symptoms of over dosage using bromelain as an oral rinse may include development of oral ulcers, stomatitis or angular chelitis) at the first visit & an oral soft tissue exam will be completed.

If a subject experiences unusual side effects or appears to be experiencing an allergic reaction the subject will immediately be excluded from the study and will seek medical care if indicated.

